The intervention period will last for 3 months, after which time patients will be followed for an additional 6 months (total of 9 months). Treatment response will be assessed at **1, 3, 6, and 9 months after the date of the first intervention session**. The primary end point will be at 3 months (immediate post-intervention). Early response will be assessed at 1 month. Sustained response will be assessed at 6 and 9 months post-randomization. POYSE will last 4 years including 3 months for start-up; 2.5 years for recruitment; **9 months** for follow-up; and 6 months for data analysis and manuscripts.

Figure 2: POYSE Trial Design

D3. STUDY SITES

The RVAMC is an urban, university-affiliated, tertiary care center in Indianapolis which provides health care for more than 53,000 veterans. As Indiana's tertiary care facility, RVAMC receives referrals from VA facilities at Ft. Wayne and Marion, Indiana, and from nearby Danville, Illinois. The RVAMC provides acute inpatient medical, surgical, psychiatric, neurological, and rehabilitation care, as well as primary and specialty outpatient services. The clinics staff 75 primary care providers (faculty and resident physicians; advance practice nurses), caring for over 20,000 patients who make over 65,000 visits per year. The RVAMC is also the parent facility to three community based outpatient clinics—the Bloomington, Terre Haute, and Martinsville Outpatients Clinics. The Bloomington and Terre Haute CBOCs staff 4 primary care providers each and 1 provider is based at Martinsville. Each site provides primary care, prescription and other services to approximately 9,500 veterans in the Bloomington, Terre Haute, and Martinsville, IN metropolitan areas (all sites approximately 1 hour drive from Indianapolis).

D4. RECRUITMENT

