Analytic techniques will be similar to those previously described. Since there will be a number of secondary outcomes, we will account for multiple-comparisons in analyses. We will use the Bonferroni approach to adjust for statistical significance threshold when the number of tests is less than 20. Otherwise, we will use the false discovery rate (FDR)¹²² to control the magnitude of false positives. We will also stratify our analysis based on a baseline depression status (PHQ-9). Our previous research indicated that 30% to 40% of patients will have clinically significant depression, which may adversely affect pain outcomes. Thus, depression is a potential moderator.

D9f. Missing data

Missing data are unavoidable in longitudinal studies. Based on our prior studies, we anticipate a possible dropout rate between 8% and 12%. However, we conservatively estimated a possible 20% drop out rate which is reflected in the sample size calculation. We will first run a logistic model with missing status as the response variable, intervention arm, patients’ demographic characteristics as covariates to check whether the missing status depends on the intervention group assignment and patient characteristics. Second, our linear mixed-effect model can accommodate missing-at-random (or

MAR which is assumed in many trials)¹²³ where no bias will be introduced by ignoring the missing-data mechanism. If drop-outs are Missing Not At Random (MNAR), meaning the likelihood of drop-out depends on an un-observed outcome, and the missing data mechanism is ignored, potential bias can be introduced. We will run sensitivity analyses using complete cases, last observation carried forward imputation, other multiple imputation methods including linear mixed-effect model, to compare results across these analyses to assess the robustness of the inference.

D9g. Economic evaluation

We will conduct cost effectiveness to determine if changes in health care utilization may offset the intervention costs between treatment arms. To conduct this analysis, we will use established methods¹²⁴ to estimate direct costs of the interventions and health care spending for study participants during the **9 month** trial period from the perspective of the VA.

D9h. Costing

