We will use both micro- and gross (average) costing methods^{125,126} to estimate intervention and health care utilization costs, respectively. Applying VA Health Economics Resource Center (HERC) guidelines, we will measure intervention-related activities and their associated costs.¹²⁵ These intervention costs will include: 1) yoga and fitness instructor average salaries plus fringe benefits; 2) study materials (yoga mats, eye pillows, DVDs, audio-recordings, ergometers, heart monitors, pedometers) provided to intervention patients; 3) parking; and 4) facility overhead.

We will use VA DSS data to obtain health care utilization and cost estimates for trial participants. From the VA Patient Treatment File (PTF), we will collect hospital discharge date, days of hospital stay, and ICD-9 diagnoses (especially primary or secondary diagnoses) of fibromyalgia for each stay and determine the cost per admission. From the Outpatient Care File (OPC), we will collect dates of any outpatient visits for fibromyalgia, location of care (stop code), CPT codes assigned to each visit, and type of provider delivering care. We will classify all visits into rehabilitation, primary care, emergency, pain, specialty medicine or surgery, mental health, and other treatments based on clinic codes.

The number of outpatient prescriptions, especially for analgesic and psychotropic medications, will be found in the DSS NDE Pharmacy Datasets from VA Information Resource Center (ViReC).¹²⁷ Laboratory and x-ray testing will be collected to determine the number of tests for fibromyalgia evaluation and the costs per test. The cost of other care will be obtained from utilization data included in VA Austin databases. For non-VA care, covered by the VA, fee basis files will be merged into DSS data.¹²⁸ For non-VA care not covered by the VA, we will rely on patient self-report of outpatient visits and hospitalizations. Since VA utilization data does not include cost estimates, the above mentioned data sets will be merged to the HERC average cost datasets to estimate the costs associated with VA utilization for each participant.^{129,130}

D9i. Analysis

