To estimate cost effectiveness, the dependent variable will consist of primary cost outcomes calculated from the VA health care system perspective. Having obtained the relevant VA healthcare utilization events, the healthcare event requires valuation, which is the task of assigning a reasonable market-level dollar for the expense amount. For each patient, outpatient events (visits, procedures, labs, medications, etc.) and inpatient DRGs and medical events (procedures, labs, medications, etc.) will be captured from these patient-specific administrative datasets. VHA databases provide sufficient outpatient and inpatient procedure and associated treatment classifications (by CPT-4, DRG and ICD-9 codes) to allow valuation. [name] has created similar datasets in other VA funded studies and publications. For health care utilization and the associated costs, we will compare inpatient days, outpatient visits, telephone care, number of prescriptions and radiographic tests. However, we may not be able to include inpatient costs because hospitalization may occur rarely during the 9 months of the trial and make estimates of between-group differences imprecise.

We will compare the two treatment arms with respect to total health care costs. Univariate, bivariate and regression techniques for repeated measures will be used to estimate the healthcare events and expenditure amounts. If cost data are skewed, log transformations will be performed prior to performing regression. An ANCOVA model will be used and contain treatment group (independent variable) and adjusted for comorbidities, age, and previous health care cost data collected at baseline as a covariate.

Costs will be reported in current year's dollars. Sensitivity analyses will be used to account for assumptions, including changes in intervention costs and changes in costs related to inpatient or outpatient services. If the interventions are found to be differentially more effective and costly, we will perform a cost-outcome analysis (i.e., incremental cost-effectiveness). We will estimate the effect of the interventions on the primary outcome (FIQR total score). The incremental cost to achieve a clinically meaningful decrease in FIQR total scores due to the interventions, i.e., the cost-effectiveness ratio, is calculated as the difference in intervention costs between the two treatment arms, divided by the difference in effectiveness between groups.

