$$\text{Intervention Costs} + (\Delta \text{ Health Care Costs})$$

$$(\Delta \text{ FIQR}_{\text{Yoga}}) - (\Delta \text{ FIQR}_{\text{Structured Exercise Program}})$$

Where Δ FIQR = change in FIQR score, and Δ Health care costs = difference two groups

D10. PROJECT MANAGEMENT PLAN

D10a. Project Timeline

The 1st quarter in year 1 will involve hiring and training personnel. Important steps will include: (1) finalizing treatment protocols for yoga and exercise arms; (2) training the research assistant in screening, enrolling, and consenting study participants; (3) programming the electronic medical records to identify potential study subjects based on fibromyalgia diagnosis; and (4) obtaining permission from individual treating physicians to approach patients of theirs who might be eligible. During the next 2.5 years, we will enroll **306** participants (randomizing **153** to each group). Enrollment will average 10 per month. The **306** participants will be treated for 3 months. Participants will have outcome assessments at baseline, **1, 3, 6, and 9 months**. Thus, enrollment will be conducted from the 2nd quarter (year 1) until the 4th quarter (year 3); the intervention phase from 2nd quarter (year 1) until 1st quarter (year 4); and outcome assessments from 2nd quarter (year 1) until the end of study period. Baseline analysis will begin at the beginning of year 4 and conducted during the final 9 months of the study (separate baseline, 3 month, and end-of-study analyses). Main reports and manuscripts will be prepared in the 3rd and 4th quarters of Year 4.

POYSE Study Timeline																
Quarters	Year 1				Year 2				Year 3				Year 4			
	1	2	3	4	1	2	3	4	1	2	3	4	1	2	3	4
Start-up																
Enrollment																
Intervention																
Assessments																
Analysis																
Manuscripts																

D10b. Overall project coordination and facilities

Overall project coordination will be led by [name] (PI) and [name] (Project coordinator). [name] will coordinate all aspects of the project, trouble-shoot any problems, and provide regular updates on recruitment progress. Drs. [name], [name], and [name] have office, meeting and research space within the HSR&D Center for Implementing Evidence-based Practice (CIEBP) at the RVAMC. [name] and [name] offices are a 5-minute walk or drive, respectively from CIEBP. [name] will be available for the monthly study-related teleconferences.

D10c. Investigator roles

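### The cost-effectiveness ratio is defined two ways in D9i: the sentence leaves health care costs out of the numerator, the formula adds them, and the formula is itself incomplete

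*Combined protocol and SAP*

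**What the plan says.** Aim 3 (section A) is to compare the cost-effectiveness of YOGA and SEP. Section D9 builds this up in four places.

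- D9g, Economic evaluation, gives the purpose: "to determine if changes in health care utilization may offset the intervention costs between treatment arms". Costs cover the 9-month trial period from the VA perspective.
- D9h, Costing, uses micro-costing and gross costing "to estimate intervention and health care utilization costs, respectively". It lists intervention costs as instructor pay, study materials, parking and facility overhead. Health care use is costed separately from VA data.
- D9i, Analysis, makes the ratio conditional: "If the interventions are found to be differentially more effective and costly". It then says that the ratio is "calculated as the difference in intervention costs between the two treatment arms, divided by the difference in effectiveness between groups".
- The formula at the end of D9i has a numerator made of an intervention cost term plus a Δ health care cost term. Its denominator is Δ FIQR for yoga minus Δ FIQR for structured exercise. The key explains Δ FIQR only as a change in score and adds "Δ Health care costs = difference two groups". It has no entry for intervention costs.

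On the cost model, D9i says "If cost data are skewed, log transformations will be performed prior to performing regression". It also says that costs will be reported in dollars.

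**The concern.** An analyst who follows the sentence leaves health care costs out of the ratio. One who follows the formula includes them. Only the second ratio bears on the offset question in D9g. If YOGA costs more to deliver but leads to less health care use, the sentence reports a price per FIQR point and gives no sign that the price may have been recovered elsewhere.

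Taking the formula as the governing text does not settle the matter, because it does not say that its first term is a difference between arms, or which direction of FIQR change counts as positive.

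The log-cost provision raises a smaller question. The numerator is a difference in mean dollars, but a regression on log costs estimates a ratio of geometric means. The plan does not connect the two.

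**Working it through.** The economic section prints no cost figure, so there is nothing to reproduce there. The check sets the definitions side by side and then illustrates them on assumed dollar values.

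**1. The two numerators.** Let I be the YOGA minus SEP intervention cost, H the YOGA minus SEP health care cost, and E the YOGA minus SEP mean FIQR improvement (baseline minus follow-up).

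- Sentence: I / E.
- Formula, with its first term read as I: (I + H) / E.
- Formula minus sentence: H / E, which is zero only when H = 0.

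**2. Illustration.** For E, take the 6.79 points printed in D9a. This is a 3-month planning value; 14% of 48.3 is 6.76, and the difference is immaterial here. Assume I = +$100 per patient and let H vary.

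- H = -$300: sentence 100/6.79 = $14.73 per point; formula -200/6.79 = -$29.46.
- H = -$100: sentence $14.73; formula $0.
- H = $0: both $14.73.
- H = +$300: sentence $14.73; formula 400/6.79 = $58.91.

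For scale, B1 cites yearly costs of $2,274 (in 1996 dollars) and $5,945. Over 9 months these are 2,274 × 0.75 = $1,706 and 5,945 × 0.75 = $4,459, so $300 is about 18% of the first and 7% of the second. Neither is an estimate for this trial.

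**3. The condition for computing the ratio.** It requires YOGA to be more effective and more costly, without saying which cost. Take I = +$100 and H = -$300, with YOGA more effective.

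- Intervention cost in both condition and ratio: the condition is met, and the ratio is +$14.73.
- Total cost in both: the total is -$200, the condition is not met, and no ratio is computed, because YOGA is better and cheaper.
- Intervention cost in the condition, total cost in the ratio: the ratio is -$29.46.

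The reverse mixture behaves likewise. With I = -$100 and H = +$300, a total-cost condition is met at +$200, the sentence gives -$14.73 and the formula +$29.46.

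**4. The formula read literally.** If the first term is YOGA's delivery cost alone, the numerator is too large by SEP's delivery cost. If it is both arms' cost added together, it is too large by twice SEP's delivery cost. Higher FIQR scores are worse (D8a), so if change means follow-up minus baseline, a better YOGA result makes the denominator negative.

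**5. Log costs, only if costs are skewed.** Assume lognormal costs with log-mean m and log-SD s. The geometric mean is exp(m) and the arithmetic mean is exp(m + s²/2).

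- Equal s in both arms: exp(s²/2) = 1.38, 1.65 and 2.05 for s = 0.8, 1.0 and 1.2. Exponentiated log means would then show 1/1.38 = 73%, 61% and 49% of the true dollar difference.
- Unequal s, with a geometric mean of $3,000 in both arms so that the log-scale effect is zero: s = 1.2 against 1.0 gives means of $6,163 and $4,946, a difference of $1,217.

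The group coefficient on the log scale therefore does not give the mean dollar difference without a further step.

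**The case against.** The strongest reply is that the intent is plain. The formula directly follows the sentence, D9g asks about offsets, and D9i compares total health care costs, so one loose phrase stands against several clear signals. That is a fair account of intent, and it makes the repair easy. It does not remove the conflict: D9h itemises intervention costs separately from health care use, so the sentence followed as written omits a component that the formula includes. The display may have suffered in PDF reading, but the key beneath it also defines no difference for intervention costs.

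A reader might infer that the two definitions by themselves give answers of opposite sign. The documents do not support that. With improvement taken as baseline minus follow-up, opposite signs arise only when the condition uses one cost definition and the ratio another. An analyst who uses one definition throughout gets a positive ratio or no ratio.

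A reader might also infer that the log transformation is an error. It is conditional, nothing says that log means will simply be exponentiated, and retransformation can recover the arithmetic mean. What stands is that the route is not stated.

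Finally, a reader might take the unnamed FIQR time point in the ratio as a defect. D9i ties effectiveness to the primary outcome, and D2 and D9c put the primary endpoint at 3 months, so there is a natural default. Stating it would be a clarification only.

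**Conclusion.** The concern holds as an inconsistency in the definition of the Aim 3 ratio. The sentence in D9i omits health care costs and cannot answer the question in D9g. The formula includes them but does not fully define its terms. If its first term is the between-arm difference, the discrepancy is exactly the health care cost difference divided by the FIQR difference. Its size in this trial cannot be found from the documents: the $100 and ±$300 figures are assumptions, and 6.79 is a planning value. Used consistently, the two definitions can still lead to different conclusions, such as a price per point under one and no ratio, because YOGA is cheaper overall, under the other.

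The log-cost point is secondary and applies only if costs are skewed. Its figures rest on lognormal costs and assumed log-SDs.

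Nothing here touches the primary FIQR analysis, the sample size or safety.

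**What to change.** Put one definition in both the sentence and the formula:

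[(YOGA minus SEP intervention cost) + (YOGA minus SEP health care cost)] / (YOGA minus SEP mean FIQR improvement), with improvement = baseline minus follow-up.

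Use the same total cost in the condition that decides whether the ratio is computed.

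For skewed costs, estimate the arithmetic mean difference directly, by untransformed regression or by a gamma GLM with log link and marginal means. If log regression is kept, state a retransformation that allows for unequal variances between arms.

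Optionally, name the FIQR time point that is set against the 9-month costs.

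The cost is a corrected sentence and formula, a few words in the condition, a sentence or two on the cost model, and a little more analysis work. No new data are needed.

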Each of the study questionnaires will be programmed into a desktop computer using Microsoft Access. The research assistant will interview the patient and enter data simultaneously into the Access program. Within the Access program, algorithms will be created to check for inappropriate or missed data entry. Computer algorithms will also automatically score the questionnaires and store the summary scales within the same database, as well as determine the appropriate date for follow-up interviews. These data will be backed up daily onto a secured server at RVAMC. Participant social security numbers, names, addresses and other personal information will be restricted to authorized personnel to protect confidentiality. For data analysis and other uses of the data, this information will be removed from the database and be replaced with a simulated identification number. This strategy has been used in our previous trials to screen and enroll patients, accurately complete follow-up assessment, and protect patient privacy. We have experience in setting up data integrity protocols and data back-up to minimize the risk for lost or inaccurate data.

D10e. Data Safety Monitoring Plan

The following multi-component Data Safety Monitoring Plan has been used in our VA RR&D-funded ESCAPE trial of OEF/OIF veterans with chronic musculoskeletal pain and NIMH-funded pain/depression SCAMP trial. Subjects are monitored during study interventions in the following ways: 1) frequent subject contacts by research team members. Responses to the interventions, as well as side effects from them are closely monitored. All interview responses are part of the study database. 2) Monthly Executive Committee Meetings. The PI and co-investigators meet monthly for Executive Committee meetings. At these meetings the investigators discuss recruitment, subject safety, protocol adherence, and any other issues that may arise. Minutes are kept and are circulated to any co-investigators not able to attend. Subjects will be allowed to withdraw from the trial at any time. If a patient withdraws, we will determine the reason for withdrawal. Possible reasons will include: 1) death, 2) worsening of comorbid medical conditions making follow-up impossible, 3) treatment side effects, and 4) other. If subjects withdraw, we will attempt to obtain their permission to complete the remaining

outcome assessments. We will establish a local Data Safety Monitoring Board (DSMB) that meets every 6 months during the study and is notified via email of all deaths and SAEs at the time of local IRB notification. Members will consist of non-study investigators and will include a pain specialist, a rheumatologist, a clinical trialist, a nurse, and a biostatistician.

The DSMB will monitor the following: (a) subject recruitment, accrual, and retention; (b) patient outcomes and adverse events; (c) subject safety, privacy, and confidentiality procedures; (d) diversity of subject enrollment (i.e., sex and race); (e) data quality and major findings in terms of treatment benefits and risks; (f) results of related studies that impact subject safety; (g) assessment of scientific reports that might alter the benefit/risk ratio of the study. Analyses of data will be performed by the study biostatistician but will be independently interpreted by the DSMB (which will include an independent biostatistician) which can request additional analyses as the DSMB members see fit. Since this is an effectiveness trial using evidence-based treatments, there are no pre-planned interim analyses or stopping rules. The DSMB will submit the report of its annual meeting to the study investigators who will in turn report the information to IRB in its continuing review, unless there are items DSMB feels should be reported to IRB immediately.

D11. DISSEMINATION AND IMPLEMENTATION PLAN

The VHA National Pain Management Strategy Coordinating Committee will serve as our primary channel for disseminating study findings to VA providers, administrators, researchers and policy makers. Findings will be disseminated to the committee in the form of summary reports and presentations given either in the monthly conference calls or at their annual face-to-face meeting (or both). The Committee will advise and coordinate next steps for dissemination, including dissemination to other relevant entities such as VISN and hospital administrators; local Pain Management Committees; the VISN Pain Points of Contact, the Office of Quality and Performance; and the national working groups related to pain management education, guideline development, and performance measures. Additionally, a summary of study findings and implications will be posted on the VHA Pain Management Committee's website in a format readable to veterans. Findings will be disseminated to our research audiences through scientific presentations and publications, and VA cyber seminars, as well as through conference calls with the Pain Research Working Group, a subcommittee of the VHA National Pain Management Strategy Coordinating Committee.

We also will seek synergistic opportunities with the Pain Research, Informatics, Medical comorbidities and Education (PRIME) Center directed by [name] (VA National Program Director for Pain Management). Other resources include a VA national pain management website; a widely subscribed VA pain list serve; monthly national educational teleconferences targeting providers and administrators; a network of VISN Pain Points of Contact who hold monthly teleconferences and who serve an important liaison role between the National Pain Management Committee and facility level pain committees; and a network of VA and non-VA pain-relevant investigators (the Pain Research Working Group) who hold twice monthly teleconferences and yearly face-to-face meetings and who, among their goals, work to promote dissemination of research findings and to influence practice and policy related to pain care. In sum, an established network of resources is already in place to disseminate study findings. Our research group has disseminated study findings in the VA Cyber-seminar forum sponsored by the Center for Information Dissemination and Education Resources (CIDER).

D12. POTENTIAL LIMITATIONS OF PROPOSED STUDY

Generalizability: The study sample will be drawn from a single, VA medical center and three VA community clinics in Indiana. As such, the sample may not be representative of all patients with fibromyalgia. However, the treatments under study could certainly be applied in other VAMCs/CBOCs.

Study design: Our research team thoroughly discussed and debated study design issues. In the end, we agreed to frame POYSE as a fully powered, 2-arm comparative effectiveness trial. However, we strongly considered a 3-arm study to compare yoga vs. structured exercise vs. wait-listed usual care. However, we rejected this alternative for two reasons. The first was pragmatic: it would be difficult to enroll a 50% greater sample size at a single site and this design would add substantially to the trial

costs. Second and more importantly, findings from our recent pain trials have demonstrated the ineffectiveness of usual care for chronic pain management, making a wait list control of less relevance.

Multi-component intervention: The POYSE trial involves a multi-component, yoga intervention that will **primarily** test the “bundled” effect (combination of yoga poses, relaxation, and meditation practices) on reduction of overall fibromyalgia severity and associated symptoms. **Determining the relative effects of the individual yoga components will be difficult, but not impossible. While we considered a study of a less complex intervention, a multi-modal approach is best suited to handle the complexities of fibromyalgia management based on the biopsychosocial model. We also considered either eliminating the meditation component completely or delivering the components sequentially in a stepped-wise fashion rather than concurrently as an integrated, mind-body, intervention. However, for historical, philosophical, and logistical reasons we decided to deliver the “bundled” yoga intervention as originally proposed.**

To help determine the relative effects and “unbundle” the individual yoga components, we propose two strategies. First, we will conduct post-study, in-depth interviews of a subsample of study participants who receive the yoga intervention. Interview questions will focus on perceptions of which yoga component was most or least helpful, which yoga exercises did participants use most (or least) at home, and patient recommendations to create a “yoga toolbox”, i.e., the yoga exercises viewed most effective to reduce fibromyalgia symptoms. Based on our experience with similar qualitative studies, we expect to conduct approximately 25 interviews to improve our understanding of the relative value patients place on the different yoga components (poses, meditation, breathing exercises). We have found qualitative work like this to be highly informative in elucidating trial results. Second, since we expect each component to be an active ingredient, we plan to quantify these components and examine whether there is a dose-response relationship between each component and the primary outcome. We will not control for differential use of components in our main analysis because our main goal is to determine the overall effectiveness of a multi-component yoga intervention.

D13. STRENGTHS AND SYNOPSIS OF STUDY

Despite the study limitations, the POYSE trial has a number of strengths, including: (1) testing the comparative effectiveness of two unique interventions designed to improve the management of fibromyalgia; (2) management approaches that challenge existing treatment paradigms for fibromyalgia care and have the potential to be applied across multiple VA clinical settings; (3) a focus on a significantly understudied fibromyalgia population (men and veterans); (4) a clinical condition that has become frustrating to VA providers; (5) a randomized clinical trial design; (6) ample statistical power to detect meaningful differences in our primary outcome; (7) a large sample size relative to previous trials of yoga and exercise; and (8) an economic evaluation that may provide VA administrators, clinical managers, and policy makers with data to inform budget decisions to invest in these interventions and make them routinely available to veterans suffering from fibromyalgia.

In sum, VA providers are faced with numerous challenges in treating patients with fibromyalgia. The interventions being tested in the POYSE trial have the potential to provide primary care settings with new treatment models that will help to guide VA providers while at the same time providing much needed relief for veterans suffering from fibromyalgia.

